Using Comparative Toxicogenomics Database to identify the top genes influenced by vitamin D supplementation in thousands of experiments. One hundred five genes with at least five documented interactions with VitD were identified. Moreover, to explore if the identified genes are sharing common pathways, Enriched Ontology Clustering for the identified genes will be performed using the Metascape (a web-based tool used for comprehensive gene list annotation and analysis resource).

In silico determination of effect of vitamin D treatment on the expression of NR3C1 and NR3C2 in monocytes, macrophages, and dendritic cells

In order to investigate the effect of VitD supplementation on the mRNA expression of NR3C1, NR3C2 and VDR, publicly available datasets (GSE52819, GSE13762, GSE56490) will be explored as they were designed to examine the global transcriptional effect of VitD supplementation on monocytes, macrophages, and dendritic cells.

In silico determination of the mRNA expression levels, and correlations, of NR3C1, NR3C2, and VDR in the blood of asthmatic patients compared to healthy controls

We will extract from publicly available datasets (GSE69683) with a large number of participants and their detailed clinical information. To find Gene expression profiling of blood from these groups was analyzed, and the gene expression of GR (NR3C1 and NR3C2) which was determined.

Patients

To do double-blinded, randomized, placebo-controlled study of VitD supplementation on 45 asthmatics with VitD deficiency will be performed. Moderate to severe asthmatics between 18 and 65 years of age who had clinician-diagnosed asthma with 25-hydroxyvitamin D3 (25 D3) level less than 20ng/mL at the screening visit will be recruited at the Rashid Hospital, Dubai, U.A.E., and the Zayed Military Hospital, Abu Dhabi, U.A.E.

mRNA expression and cytokine expression

Whole blood will be collected in PAXgene tubes (Qiagen, Germany) for the isolation of cellular RNA. Blood specimens will be assessed for mRNA expression of Glucocorticoid receptor (GR- β and

GR- α) using qRT-PCR. Bioplex multiplex immunoassay (BioRad, CA, USA) will use to assess the protein expression of IL-17A, IL-17-F, IFN- γ , IL-4, IL-5 and TNF- α in serum obtained from patients before and after treatment.

Statistical Analysis

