Standard statistical t-tests and one-way ANOVA will be performed to test for statistical significance between data groups using GraphPad Prism 8 (GraphPad, San Diego, CA, USA). $p < 0.05$ was considered significant.

To whom it may concern

Date : 15/06/2020

Subject : Vitamin D Regulates the Expression of Glucocorticoid Receptors in Blood of Severe Asthmatic Patients

I am [name] ,Principle investigator for the study (Vitamin D Regulates the Expression of Glucocorticoid Receptors in Blood of Severe Asthmatic Patients) . I am confirming that the results is relevant to the study in the record.

Results :

Top Vitamin D regulated pathways are involved in response to Steroids

To identify VitD targeted enriched pathways, we analyzed Comparative Toxicogenomics Database from thousands of experiments. Interestingly, the top enriched pathways regulated by VitD were involved in several metabolic and inflammatory processes including response to steroids, lipopolysaccharide as well as Interleukin-4, Interleukin-13 and AGE-RAGE signalling (Suppl. Figure 1). Many of those VitD targeted pathways were also targets of dexamethasone. These include pathways involved in inflammation; proliferation; pro-apoptosis, beside others (Figure S1).

VDR, NR3C1 and NR3C2 expression levels in different types of immune cells

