Activated T cells was shown to upregulate VDR, while treatment with VitD suppressed the proliferation of these cells, as well as their ability to produce IFN- γ and IL-17 cytokines.¹⁸ The level of expression of VDR in the blood of asthmatic and its association with the expression of steroid receptors relative to disease severity was not determined. To investigate that, we analyzed the expression profile of publicly available datasets (GSE69683) which has a large number of participants and detailed clinical information. A total number of 498 participants, of which 87 healthy controls, 77 moderate asthma, and 246 non-smokers severe asthma were included in the U-BIOPRED study. The differential expression of NR3C1, NR3C2, and VDR genes in the blood of patients from all groups was then determined. Patients with moderate asthma had higher levels of NR3C1 mRNA expression compared to health controls, although not to a significant level (\log_2 intensity 10.17 ± 0.29 ; $p=0.07$) (Figure 2A). When compared to moderate asthmatics, the expression of this gene, however, was significantly downregulated in severe asthmatic (\log_2 intensity 10.14 ± 0.23 versus 10.26 ± 0.21 ; $p<0.01$). NR3C2 mRNA expression was significantly downregulated in severe asthmatic compared to moderate asthma (\log_2 intensity 5.397 ± 0.727 versus 5.62 ± 0.5011 , $p<0.01$), and to healthy controls (\log_2 intensity 5.575 ± 0.5894 versus 5.397 ± 0.727 , $p=0.03$) (Figure 2B). Moderate asthmatics showed higher NR3C2 mRNA expression than healthy controls, although the difference was not significant. On the other hand, VDR mRNA expression was significantly upregulated in severe asthmatics compared to healthy controls (\log_2 intensity 8.386 ± 0.46 versus 8.206 ± 0.44 $p<0.01$), but not to moderate asthmatics (Figure 2C). Interestingly, NR3C1 mRNA expression correlated positively (Spearman $r = 0.11$, 95% confident interval=0.02007 to 0.1988 and $p = 0.01$) (Figure 2D), while NR3C2 expression correlated

negatively (Spearman $r = -0.55$, 95% confident interval = -0.5724 to -0.438 and $p < 0.0001$) with the levels of VDR expression in blood (Figure 2E).

[figure not shown]

Figure 2: NR3C1, NR3C2 and VDR mRNA expression level in the blood of subjects with severe asthma, moderate asthma, and non-asthmatics. Data was collected in the U-BIOPRED study (GSE69683).

Supplementation of vitamin D selectively favours the upregulation of GR- α receptor

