To validate the *in silico* findings, a double-blinded, randomized, placebo-controlled study was performed to test the effect of VitD supplementation on 45 vitamin D deficient asthmatics. Moderate to severe asthmatics between 18 and 65 years of age who were diagnosed with asthma and VitD (25D3) levels less than 20ng/mL at the screening visit were recruited at two hospitals in UAE (Rashid Hospital, Dubai, U.A.E. and Zayed Military Hospital, Abu Dhabi, U.A.E.). The patients were divided into two groups, an experimental group and a placebo group. The baseline serum levels of VitD in the experimental and placebo groups were comparable (11.74 ± 0.77 ng/mL, 12.96 ± 1.29 ng/mL, respectively). The experimental group received 50, 000 IU of VitD

oral supplementation weekly for eight weeks ¹⁹. Following treatment, a 2.84 ± 0.01 -fold increase in blood VitD D levels (33.34 ± 2.04 ng/mL) was observed (Figure 3). The level of VitD in the placebo group did not change (14.45 ± 1.61 ng/mL) (Table 1 and Figure 3). This result indicated that the regimen used was effective to correct VitD deficiency.

Table 1: Clinical characteristics of patients received vitamin D or placebo for eight weeks.

| Variable | Total | Placebo | Vitamin D |
|--|------------------|------------------|------------------|
| Total | 54 | 20 | 34 |
| Male | 19 (35%) | 4 (20%) | 15 (44%) |
| Female | 35 (64.8%) | 16 (80%) | 19 (55.8%) |
| Age (years) | 38.64 ± 1.90 | 40.60 ± 2.97 | 37.45 ± 2.48 |
| Body Mass Index | 32.27 ± 0.92 | 32.32 ± 5.52 | 32.32 ± 1.28 |
| Pre-treatment 25D₃ levels (ng/mL) | | 12.96 ± 1.29 | 11.74 ± 0.77 |
| Post treatment 25D₃ levels (ng/mL) | | 14.45 ± 1.61 | 33.34 ± 2.04 |

[figure not shown]

Figure 3: Pre-treatment and post-treatment levels of serum vitamin D (25D3) in patients who received vitamin D or placebo for eight weeks. Severe asthmatic patients with vitamin deficiency were divided into 2 groups. 23 patients received 50000 IV of Vitamin D orally over 8 weeks, while 22 patients received placebo. Vitamin D levels were measured in the blood of these patients before and after the treatment.

We next determined whether VitD supplementation affects the gene expression of steroid receptor GR- α or GR- β . Correction of VitD levels lead to a significant increase in the expression of GR- α

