when compared to baseline level. A significant increase was observed following treatment with VitD compared to pre-treatment levels (1.89 ± 0.56 , 5.34 ± 1.40 , respectively; $p<0.05$) (Figure 4A). Moreover, there was a significant increase in GR- α expression in patients who received VitD compared to those who received the placebo control (5.34 ± 1.40 versus 1.64 ± 0.76 -fold; $p<0.05$). Interestingly, no change in GR- β expression was observed following treatment with VitD (1.49 ± 0.27 versus 1.30 ± 0.25) (Figure 4B). Relatively, the GR- α /GR- β ratio increased significantly following VitD supplementation compared to pre-treatment levels (3.58 ± 0.83 folds; $p<0.05$); or patients who received a placebo (Figure 4C).

[figure not shown]

Figure 4: Vitamin D treatment increases the expression of GR- α with no effect on GR- β .

Asthmatic subjects were treated with 50,000 IU of vitamin D orally or placebo for eight weeks. Blood specimens obtained following 8 weeks of treatment were analyzed for mRNA expression of GR- α (A), GR- β (B) using RT qPCR and the ratio of GR- α /GR- β was calculated (C). * $p<0.05$

Vitamin D supplementation downregulated the blood levels of IL-17 and IL-4 cytokines in asthmatic patients

The effect of VitD supplementation on the blood levels of asthma related pro-inflammatory cytokines was then determined (Figure 5)²⁰. Blood levels of IL-17A, IL-17F, IFN- γ , IL-4, IL-5, and TNF- α were determined before and after VitD supplementation using ELISA assay (Figure 5). VitD preferentially suppressed the blood levels of IL-17F cytokine ($p=0.04$) without affecting IL-17A; while there was no significant difference in the placebo group ($p=0.17$). A decrease in blood IL-4 cytokine levels was observed following treatment, however, not to a significant level ($p=0.07$). No significant effect of VitD supplementation was observed on the rest of the cytokines tested.

References

- 1 Palacios, C. & Gonzalez, L. Is vitamin D deficiency a major global public health problem? *J Steroid Biochem Mol Biol* **144 Pt A**, 138-145, doi:10.1016/j.jsbmb.2013.11.003 (2014).

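### The planned standard t-tests and one-way ANOVA, if pooled-variance as usual, lose power where group sizes and spreads both differ; Welch versions should be named

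*Combined protocol and SAP*

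**What the plan says.** The Statistical Analysis section is two sentences long. The first reads "Standard statistical t-tests and one-way ANOVA will be performed to test for statistical significance between data groups" and names the software; the second sets the threshold at 0.05. Pooled or unequal-variance form, checks of assumptions, transformation and sidedness are all left open.

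The results in the same document give the figures these tests were applied to:

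- GR-α after treatment, vitamin D versus placebo: "5.34 ± 1.40 versus 1.64 ± 0.76" fold, reported as p<0.05. No group sizes are attached, and ± is not defined.
- NR3C2 in the public dataset, severe versus moderate asthma: "5.397 ± 0.727 versus 5.62 ± 0.5011", reported as p<0.01. Severe versus healthy is reported as p=0.03.

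The trial's group sizes conflict. The Patients section plans "VitD supplementation on 45 asthmatics with VitD deficiency will be performed". Table 1 lists 34 on vitamin D and 20 on placebo (54 in all). The Figure 3 legend has 23 on vitamin D, "while 22 patients received placebo" (45 in all).

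**The concern.** The ordinary t-test and one-way ANOVA estimate one common variance. With equal group sizes, unequal spread does little harm. With unequal sizes it does: when the larger group has the larger spread, the pooled standard error is too big, and the test rejects too rarely and loses power; in the opposite arrangement it rejects too often.

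The steroid receptor genes and GR-α are both listed under the primary outcomes. If the comparison behind a primary outcome uses a standard error that does not match the data, the 0.05 threshold no longer means what it says, and real differences are easier to miss. For GR-α there is a further consequence: the pooled verdict can fall on either side of 0.05 depending on which of the two printed sets of group sizes is used.

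**Working it through.** **Inputs.** NR3C2 (results section on VDR and steroid receptor genes): severe 5.397, 0.727, n=246; moderate 5.62, 0.5011, n=77; healthy 5.575, 0.5894, n=87. Here ± is read as an SD; as a standard error it would imply an SD of 0.727×√246 = 11.4 log2 units for severe asthma, which is not credible.

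GR-α (results section on GR-α): 5.34 ± 1.40 and 1.64 ± 0.76. Here ± is assumed to be a standard error. Age in Table 1 supports this: 2.97×√20 = 13.3 and 2.48×√34 = 14.5 years are plausible SDs for ages 18 to 65. The support is not complete, since the placebo BMI entry of ± 5.52 looks like an SD. All tests are two-sided.

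**Formulas.** Pooled: SE = s_p√(1/n₁+1/n₂), with s_p² = [(n₁−1)s₁²+(n₂−1)s₂²]/(n₁+n₂−2). Welch: SE = √(s₁²/n₁+s₂²/n₂), with Welch–Satterthwaite degrees of freedom.

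**1. The printed GR-α result.** The difference is 5.34−1.64 = 3.70.

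| Sizes | SDs | Pooled SE, t, p | Welch SE, t, p |
|---|---|---|---|
| 34/20 | 1.40√34 = 8.16; 0.76√20 = 3.40 | 1.922, 1.93, 0.060 | 1.593, 2.32, 0.024 |
| 23/22 | 1.40√23 = 6.71; 0.76√22 = 3.56 | 1.613, 2.29, 0.027 | 1.593, 2.32, 0.026 |

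Under the standard-error reading, the Welch SE is √(1.40²+0.76²) = 1.593 whatever the group sizes, so the Welch result hardly moves. The pooled test reproduces the printed p<0.05 at 23/22 but not at 34/20. If ± is an SD, every version gives p below 10⁻¹².

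The spread is unequal under either reading of ±: the SD ratio is 2.40 (34/20, standard error), 1.88 (23/22, standard error) or 1.84 (SD), with variance-ratio p between 0.0002 and 0.007.

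**2. The printed NR3C2 results.**

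| Contrast | Difference | Pooled SE, p | Welch SE, p | Printed |
|---|---|---|---|---|
| Severe–moderate | 0.223 | 0.0888, 0.013 | 0.0735, 0.003 | p<0.01 |
| Severe–healthy | 0.178 | 0.0866, 0.041 | 0.0784, 0.024 | p=0.03 |

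**3. True level of the pooled test at nominal 5%** (simulated, normal data).

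- NR3C2 severe–moderate: 1.8%. Check: the pooled SE is too large by 0.0888/0.0735 = 1.21, so rejection needs a true z of about 1.96×1.21 = 2.37, a two-sided tail of 1.8%.
- NR3C2 severe–healthy: 3.1%.
- GR-α at 34/20: 2.0%; at 23/22: 4.9%.
- Welch's test: about 5.0% in each of these settings.

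**4. Power at the observed GR-α difference** (normal data). At 34/20: 47% pooled, 62% Welch. At 23/22: 61.3% and 61.6%.

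**5. Shape of the GR-α data.** At 34/20 the SD exceeds the mean in both arms (8.16/5.34 = 1.53; 3.40/1.64 = 2.07). On a positive fold scale that indicates strong skew. If the data were lognormal, the log-scale SDs, √ln(1+CV²), would be 1.10 and 1.29 at 34/20, and 0.97 and 1.32 at 23/22. In a lognormal simulation with equal means at 34/20, Welch on the raw scale ran at 6.5% and the pooled test at 4.6%.

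**The case against.** Several points on the other side stand.

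- The p=0.060 comes from the very test being criticised, under one reading of ± and one of two conflicting sets of sizes. No document says that the pooled test was run at 34/20. The 23/22 split matches the planned 45.
- Pooling is the usual meaning of a standard t-test, but the plan does not state it.
- Not every comparison is affected. NR3C1 severe versus moderate (0.23 and 0.21) and VDR severe versus healthy (0.46 and 0.44) have similar spreads. In both of these and in both NR3C2 contrasts, pooled and Welch fall on the same side of 0.05.
- Welch is no cure for skew, as step 5 shows, so it cannot be the whole remedy for raw GR-α fold changes.

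Three stronger readings are tempting, and the documents do not support them.

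- *The GR-α effect is spurious.* The test that allows for unequal spread gives p=0.024 or 0.026, in line with the printed p<0.05.
- *False positives are inflated.* In the contrasts worked above the larger group has the larger spread, so the normal-theory error is towards caution, and at 23/22 the level is held. NR3C1 severe versus healthy could run the other way, but that contrast is not reported, and the healthy group's spread would have to be inferred.
- *The printed NR3C2 p-values reveal which test was run.* They do not. The p<0.01 fits Welch, but 0.03 lies between the pooled and Welch values. A common error SD over the three groups, √[(245×0.727²+76×0.5011²+86×0.5894²)/407] = 0.662, gives unadjusted p=0.010 and 0.032, close to both printed values.

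**Conclusion.** The point holds in a limited form. Pooled-variance tests are a poor choice for the comparisons in which both size and spread differ. For NR3C2 the true level falls to 1.8% and 3.1%; this needs neither the standard-error reading nor the disputed trial sizes, only ± as SD and roughly normal log2 values. For GR-α the loss (level about 2%, 15 percentage points of power, p=0.060 instead of 0.024) applies only if ± is a standard error and 34/20 is the analysed split, and the level and power figures also assume normal data. At 23/22 there is nothing to choose between the tests. The harm is lost power, and a pooled verdict on a primary outcome that depends on unresolved group sizes; no reported conclusion is overturned.

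**What to change.** Replace the sentence on tests with a rule along these lines: comparisons of two independent groups use Welch's t-test; comparisons of three groups use Welch's ANOVA followed by an unequal-variance pairwise procedure such as Games–Howell; GR-α fold changes are analysed on the log scale, with Welch's test applied there, since the log-scale spreads may still differ.

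Define ± at each place it is used, reconcile 34/20 with 23/22, and state the number analysed for GR-α. Then recompute the GR-α, NR3C1 and NR3C2 p-values under that one rule, reporting exact values, and state that the rule was fixed after the results were known.

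The cost is a few lines in the Statistical Analysis section and a re-run on existing data. The loss of power where variances are in fact equal is negligible. On the log scale the GR-α effect becomes a ratio of geometric means, which the report should say.

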The level of expression of GR coding gene (NR3C1), mineralosteroid receptor coding gene (NR3C2)¹⁷, and VDR were then determined in different immune cells. NR3C1 had a significantly higher level of expression compared to VDR and NR3C2 in different types of immune cells (Figure 1). Among all cells, its expression was significantly higher on Th2 CD4 cells (215.9 TPM). Classical (94.5 TPM) and non-classical monocytes (46.7 TPM) had the highest VDR expression among all inflammatory cells. Moreover, the expression of all three genes was higher in non-classical monocytes compared to classical ones (2.0, 1.49, and 1.21 folds, respectively). Naïve CD8 T (74.1 TPM) cells and Th1/17 CD4 cells on the other hand (64.7 TPM) had the highest NR3C2 mRNA expression among all immune cells. On the other hand, activation of T cells seems to induce the expression of VDR and NR3C1, but not NR3C2 genes. Activated CD8 T cells express higher VDR and NR3C1 (10.6 and 1.47 respectively) and lower NR3C2 (0.12-fold), compared to naïve cells. Similarly, activated CD4 T cells express higher VDR, and NR3C1 (3.95 and 1.25 respectively) and lower NR3C2 (0.11-fold), compared to naïve CD4 T cells (Figure 1).

[figure not shown]

Figure 1: NR3C1, NR3C2 and VDR mRNA expression level in immune cells. Data was extracted using publicly available “Database of Immune Cell Expression, Expression quantitative trait loci (eQTLs) and Epigenomics”.

VDR and steroid receptors genes are downregulated in asthma relative to severity

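### A Results heading reports VDR as falling with asthma severity while the text beneath it reports a significant rise, and the NR3C2–VDR correlation does not match its own 95% interval

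*Combined protocol and SAP*

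**What the plan says.** The plan (Materials and Methods, third in silico subsection) sets out to determine the "mRNA expression levels, and correlations, of NR3C1, NR3C2, and VDR in the blood of asthmatic patients compared to healthy controls", using GSE69683. The Results section that answers it is headed "VDR and steroid receptors genes are downregulated in asthma relative to severity".

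The text under that heading starts from "A total number of 498 participants", and names 87 healthy controls, 77 with moderate asthma and 246 non-smokers with severe asthma. It then reports, gene by gene:

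- **NR3C1**, severe against moderate asthma: "the expression of this gene, however, was significantly downregulated in severe asthmatic" (10.14 ± 0.23 against 10.26 ± 0.21, p<0.01). No severe-against-healthy test is given.
- **NR3C2**: lower in severe asthma than in moderate asthma (5.397 ± 0.727 against 5.62 ± 0.5011, p<0.01) and than in healthy controls (5.575 ± 0.5894, p=0.03).
- **VDR**: "VDR mRNA expression was significantly upregulated in severe asthmatics compared to healthy controls" (8.386 ± 0.46 against 8.206 ± 0.44, p<0.01), "but not to moderate asthmatics (Figure 2C").

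Two correlations with VDR follow. For NR3C1: "Spearman $r = 0.11$, 95% confident interval=0.02007 to 0.1988". For NR3C2: "Spearman $r = -0.55$, 95% confident interval = -0.5724 to -0.438".

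**The concern.** There are two separate faults in one section.

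First, the heading lists VDR among the downregulated genes, but the only significant VDR result beneath it is an increase. The heading is the stated conclusion of a planned analysis, so anyone who reads or cites it alone takes away the opposite VDR result. The same section says that VDR expression in relation to severity had not previously been determined, and offers this analysis as the answer.

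Second, an interval for a correlation built on the Fisher z scale should be symmetric about the estimate on that scale. The printed r = -0.55 sits close to the lower limit and far from the upper one. This is the stronger of the two reported correlations, and it cannot be cited as printed while the estimate and its interval disagree.

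**Working it through.** **Inputs.** All come from the Results section on GSE69683: the group sizes, means and ± values, and the two correlations with their limits. I assume that ± is an SD in this section, that the severe group in the tests is the 246 non-smokers, and that tests are two-sided.

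**1. Direction for VDR**

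- Difference: 8.386 − 8.206 = +0.18 log2 units; 2^0.18 = 1.13-fold.
- Unpooled SE: √(0.46²/246 + 0.44²/87) = 0.0555.
- 95% CI: 0.18 ± 1.96 × 0.0555 = 0.071 to 0.289.
- Welch t = 3.24, p = 0.0015; pooled t = 3.17, p = 0.0017.

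The stated p<0.01 is reproduced, in the upward direction. The body text is internally consistent and the heading is the outlier.

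The same check on the other two genes shows where the heading does hold:

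| Comparison | Difference (log2) | Pooled p | Welch p | Stated p |
|---|---|---|---|---|
| NR3C1, severe − moderate | -0.12 | <0.0001 | <0.0001 | <0.01 |
| NR3C2, severe − moderate | -0.223 | 0.013 | 0.003 | <0.01 |
| NR3C2, severe − healthy | -0.178 | 0.041 | 0.024 | 0.03 |

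**2. Correlations and their intervals**

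The formula is tanh(atanh(r) ± 1.96 × SE), with SE = √(1.06/(n − 3)), the usual variance for a Spearman coefficient.

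*Control: NR3C1–VDR.* With r = 0.11 and n = 498 the formula gives 0.0197 to 0.1985, against the printed 0.02007 to 0.1988. Working back from the printed limits, the centre is r = 0.110, the SE is 0.0463, and n = 3 + 1.06/SE² = 497.9. Both the method and n = 498 are confirmed from the document itself.

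*NR3C2–VDR.* Working back from the printed limits:

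- atanh(-0.5724) = -0.6511 and atanh(-0.438) = -0.4698; their mean is -0.5604.
- Centre: tanh(-0.5604) = -0.508.
- SE = (0.6511 − 0.4698)/(2 × 1.96) = 0.0463, so n = 498.4.

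The limits are therefore those of r = -0.508 at n = 498. Working forward from the printed estimate:

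- r = -0.55, n = 498: -0.610 to -0.484.
- r = -0.545 gives -0.606 to -0.478 and r = -0.555 gives -0.615 to -0.489, so rounding of r does not explain the difference.
- atanh(-0.55) = -0.6184. It lies 0.033 (0.7 SE) from the lower limit and 0.149 (3.2 SE) from the upper, where the two distances should be equal at 1.96 SE.

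Other standard variance formulas, and n = 410, 323 or 246, do not help: the lower limit around -0.55 is always -0.608 or below, never -0.5724. In r² the discrepancy is 0.30 (from -0.55) against 0.26 (from -0.508).

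**The case against.** The best case on the other side is about weight. Both slips are in the narrative of a secondary analysis of public data; no design choice, sample size or trial endpoint depends on them. The primary outcome on severity names the steroid receptor genes and not VDR. The text directly beneath the heading gives VDR in the right direction and presents it as a contrast to the other two genes. All of that is true, and it is why this is a correction to the report and no more. It does not make the heading right.

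Two narrower objections stand. The contradiction is shown only for severe asthma against healthy controls. Against moderate asthma the text reports no significant increase and gives no means, so on that contrast the heading is unsupported and not shown to be reversed. Also, because the printed limits recover exactly the stated 498 participants, r is the likelier misprint, with a value near -0.51. That is an inference, and only the source output can settle it. A digit misread when the PDF was converted to text is also possible, and the same look at the output would reveal it.

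The three named groups sum to 87 + 77 + 246 = 410, leaving 88 of the 498 undescribed. If those 88 were counted as severe (n = 334), the VDR p-value would be about 0.001, so the conclusion does not depend on that choice.

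**Conclusion.** Both points hold. For VDR the heading contradicts the result it summarises: the reported difference is +0.18 log2 units (95% CI 0.07 to 0.29) in severe asthma against healthy controls, and no decrease is reported anywhere in the section. The heading is right for NR3C2 and partly right for NR3C1. The NR3C2–VDR estimate and its interval cannot both be correct at n = 498; they are about 0.04 apart in r.

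The VDR figures rest on reading ± as an SD and on the stated group sizes. The correlation finding rests on a Fisher-z interval, which the companion correlation supports. The negative sign and the p<0.0001 of the NR3C2–VDR correlation survive either correction, and the randomised comparison of vitamin D with placebo is unaffected.

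**What to change.** - Reword the heading to follow the reported tests: NR3C1 and NR3C2 are lower in severe than in moderate asthma, NR3C2 is also lower in severe asthma than in healthy controls, and VDR is higher in severe asthma than in healthy controls.
- Check the NR3C2–VDR coefficient and its interval against the source output, correct whichever is wrong, and print n beside both correlations.
- Label the group to which the NR3C1 value 10.17 ± 0.29 belongs. Its sentence compares moderate asthma with healthy controls but gives one mean. Reading it as the healthy group gives p = 0.023 to 0.026 for that comparison, against the stated 0.07, so I have not relied on it.

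The cost is one heading, one figure checked against existing output, and three labels. No new analysis is required.

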Steroid resistance, as documented in cases of severe asthma, is associated with increased expression of the glucocorticoid receptor (GR)- β , which is an alternative splicing isoform and dominant-negative regulator of the GR- α ¹⁴. The abundance of GR- α mRNA is higher than GR- β mRNA in all normal tissues and cells. Normally, default splicing pathway leads to GR- α , while the alternative

splicing pathway that leads to GR- β is minimally activated ¹⁵. The latter pathway, however, seems to be upregulated in severe asthmatic patients ¹⁶. In chronic inflammatory diseases like asthma, upregulated blood levels of inflammatory cytokines can participate in glucocorticoid resistance and impaired GR function by modulating its translocation, DNA binding, and GR phosphorylation status [18].

As data from observational studies suggested a better control of asthma following restoration of VitD levels.

Hypothesis:

Correcting VitD levels in adult asthmatic patients could enhance steroid responsiveness by regulating blood GR- α /GR- β ratio levels.

Primary Out comes:

1. To find out the top pathways regulate Vitamin D

identify VitD targeted enriched pathways, we analyzed Comparative Toxicogenomics .Enriched Ontology Clustering for the identified genes was performed using the Metascape (a web-based tool used for comprehensive gene list annotation and analysis resource)Database from thousands of experiments.[Time Frame: 8 weeks]

2. To examine asthma severity in relation to steroid receptors genes [Time Frame: 8 weeks]

3. study the effect of vitamin D on GR- α receptor [Time Frame: 8 weeks]

4. study the effects of Vitamin D on cytokines. [Time Frame: 8 weeks]

Inclusion Criteria:

- Diagnosis of asthma
- age group between 18 and 65 years
- low level of 25-hydroxyvitamin D3 (25 D3) level less than 20ng/mL

Exclusion Criteria:

- smoker patients
- less than 18 years old
- patient on Vitamin D supplementation already

Materials and Methods

In silico identification of top genes regulated by vitamin D supplementation

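### The results heading says the steroid receptor genes are downregulated in asthma, but the printed figures show no reduction of NR3C1 against healthy controls, and NR3C2 is lower than healthy only in severe asthma

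*Combined protocol and SAP*

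**What the plan says.** Primary outcome 2 is "To examine asthma severity in relation to steroid receptors genes". The third in silico subsection of Materials and Methods plans to examine expression of NR3C1, NR3C2 and VDR "in the blood of asthmatic patients compared to healthy controls", using GSE69683. It does not say whether moderate and severe asthma are to be pooled. Under Statistical Analysis, "Standard statistical t-tests and one-way ANOVA will be performed to test for statistical significance between data groups", at the 0.05 level. The t-test variant and any post-hoc or multiplicity method are not given.

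The results section is headed "VDR and steroid receptors genes are downregulated in asthma relative to severity". For the two steroid receptor genes, its text reports:

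- NR3C1, moderate versus healthy: "Patients with moderate asthma had higher levels of NR3C1 mRNA expression compared to health controls, although not to a significant level" (one mean printed, 10.17 ± 0.29; p = 0.07).
- NR3C1, severe versus moderate: "the expression of this gene, however, was significantly downregulated in severe asthmatic" (10.14 ± 0.23 against 10.26 ± 0.21; p < 0.01).
- NR3C1, severe versus healthy: nothing in the text.
- NR3C2, severe versus moderate: lower (5.397 ± 0.727 against 5.62 ± 0.5011; p < 0.01).
- NR3C2, severe versus healthy: lower (5.397 against 5.575 ± 0.5894; p = 0.03).
- NR3C2, moderate versus healthy: higher, not significant.

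**The concern.** The heading acts as the conclusion for primary outcome 2. A reader will take from it that glucocorticoid receptor gene expression is reduced in asthma and falls with severity. The text beneath does not report that pattern. Moderate asthma lies above healthy controls for both steroid receptor genes. The one significant NR3C1 result compares severe asthma with that raised moderate group, not with healthy controls. Severe versus healthy is reported for NR3C2 and VDR but is missing from the text for NR3C1, the gene that the study title is about. What is at stake is whether one of the four primary outcomes carries a conclusion that its own figures do not show.

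**Working it through.** **Inputs** (results text on GSE69683). Group sizes are healthy 87, moderate 77, severe non-smokers 246. Means and ± values are as listed above. All tests are two-sided.

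**Assumptions.**
- ± is a standard deviation. As a standard error, severe versus moderate NR3C1 would give t = 0.12 / √(0.23² + 0.21²) = 0.12 / 0.311 = 0.39, which cannot yield p < 0.01.
- 10.17 ± 0.29 is the healthy group, because the next sentence gives moderate asthma as 10.26 ± 0.21.

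**Step 1: reproduce the printed p-values.**

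| Contrast | Printed p | Recomputed p |
|---|---|---|
| NR3C2 severe vs healthy | 0.03 | 0.032 (ANOVA, Fisher LSD); 0.024 Welch; 0.041 Student; 0.080 Tukey |
| NR3C2 severe vs moderate | <0.01 | 0.003 Welch; 0.013 Student; 0.010 LSD |
| NR3C1 severe vs moderate | <0.01 | below 0.001 in every variant |
| NR3C1 moderate vs healthy | 0.07 | 0.023 Welch; 0.026 Student; 0.017 LSD; 0.045 Tukey |

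The last row does not reproduce. Only a threefold Bonferroni adjustment comes close (3 × 0.023 = 0.069). No single method reproduces all the printed values.

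**Step 2: the missing NR3C1 contrast, severe versus healthy.**
- Difference = 10.14 - 10.17 = -0.03 log2.
- Welch SE = √(0.29²/87 + 0.23²/246) = √(0.000967 + 0.000215) = 0.0344.
- t = -0.03 / 0.0344 = -0.87, p = 0.38. The pooled-variance test gives p = 0.33.
- 95% CI about -0.098 to 0.038. As a ratio, 2^(-0.03) = 0.98 (0.93 to 1.03).

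**Step 3: does this depend on the healthy mean?**
- Setting the healthy mean to 10.19 brings moderate versus healthy to p = 0.076 to 0.082, close to the printed 0.07. Severe versus healthy is then -0.05, with p = 0.11 to 0.15.
- If 10.17 were instead a moderate-asthma mean, healthy would lie below 10.17, because the text says moderate is the higher. Severe asthma would then be less than 0.03 below healthy, or not below it at all.

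**Step 4: an overall asthma group, as a supplement only.**
- NR3C1: (77 × 10.26 + 246 × 10.14) / 323 = 10.169 against 10.17; p about 0.97.
- NR3C2: (77 × 5.62 + 246 × 5.397) / 323 = 5.450 against 5.575; difference -0.125 (95% CI about -0.27 to 0.02); p = 0.09 Welch, 0.12 Student.
- Weighting the two severities equally gives +0.03 for NR3C1 (p 0.32 to 0.38) and -0.07 for NR3C2 (p 0.36 to 0.42).
- The three groups sum to 410 of 498, so 88 participants have no printed data. If they resembled the severe group, the overall p would be about 0.8 for NR3C1 and 0.06 to 0.09 for NR3C2.

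**The case against.** The heading carries a qualifier about severity, and outcome 2 is about severity. Both steroid receptor genes are reported lower in severe than in moderate asthma, and NR3C2 is lower in severe asthma than in healthy controls. That is real support for part of the heading, and it stands. It does not cover a claim of downregulation in asthma for NR3C1.

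Three stronger readings are tempting, and the documents do not support them.

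- **That a planned comparison was left out.** The methods never specify a pooled asthma group, planning one-way ANOVA fits several groups, and comparisons with healthy controls are reported by severity. The gap among the steroid receptor pairwise results is NR3C1 severe versus healthy. Even that is a gap in the text only: Figure 2A is not reproduced here and may show it.
- **That both genes are null in asthma overall.** For NR3C2, p = 0.09 to 0.12 with an interval reaching -0.27 is not significant, which is different from evidence of no difference. The two severities lie on opposite sides of healthy, so the pooled figure reflects the 77:246 mix and averages away the pattern that outcome 2 asks about.
- **That the trial's rationale falls with the heading.** The hypothesis concerns the GR-α/GR-β ratio, and the introduction cites raised GR-β in steroid resistance. The results do introduce the trial as validating the in silico findings, but they do not say that reduced receptor expression in asthma is among them. The vitamin D pathway result is an equally natural referent.

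**Conclusion.** The point holds in a limited form. The heading overstates the steroid receptor results. For NR3C1 no reduction against healthy controls is shown: moderate asthma is reported higher, and severe asthma recomputes to 0.03 log2 lower, about 2%, with an interval that includes zero. For NR3C2 the reduction against healthy is confined to severe asthma. It is significant without adjustment (0.024 to 0.041) but not under Tukey (0.080).

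The NR3C1 estimate rests on reading ± as a standard deviation and 10.17 ± 0.29 as the healthy group. The failure to reproduce p = 0.07 leaves doubt about the group or the test, so confidence is moderate. The sensitivity checks do not restore the heading. The severity of the point is also moderate: it affects the conclusion for one primary outcome, drawn from a public dataset, and no randomised comparison. Separately, the heading also lists VDR as downregulated, while the text reports it significantly higher in severe asthma than in healthy controls.

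**What to change.** - Report NR3C1 severe versus healthy with its estimate and 95% CI, alongside the other contrasts of each severity with healthy controls.
- State which group 10.17 ± 0.29 describes, what ± denotes, and which test and adjustment gave each p-value, including p = 0.07.
- Restate the outcome 2 conclusion, and reword the heading to match: NR3C1 is lower in severe than in moderate asthma but is not shown to differ from healthy controls; NR3C2 is lower in severe asthma than in moderate asthma and in healthy controls.
- An overall asthma-versus-healthy contrast is optional. If given, label it supplementary and note that it depends on the severity mix.

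The cost is one extra contrast on data already extracted, some clarifying text, and a less favourable heading.
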